## 10 STATISTICS

## 10.1 SAMPLE SIZE ESTIMATE

This is a randomized open label multi-center Phase III adaptive trial using a group sequential design with a primary end-point of OS.

The study is designed to detect a 4 months increase in median OS time from 9 months in the control arm to 13 months in the TheraSphere arm (i.e., hazard ratio = 0.69), using a log rank test.

A maximum of 250 deaths will yield 80% power to detect the target difference in median OS (i.e., HR = 0.69) with a two-sided alpha of 0.05 using a group sequential design with 2 interim analyses and stopping boundary defined by the rho family error spending function with rho=1.5 (Jennison and Turnbull, 200025). It is estimated that a maximum of 320 patients will need to be recruited over 42 months, with a 1 year additional follow-up period. This includes an adjustment to take account of an assumed 5% of patients who will be lost to follow-up and for whom a date of death is not recorded.

Sample size modification will be considered at the second interim analysis using the approach described in Mehta and Pocock (2011), which employs an un-weighted test statistic at the final analysis as recommended by Burman and Sonneson (2006). If the sample size is increased after the second interim analysis, the final analysis is planned when approximately, but no less than, 430 deaths have occurred, which will result in 80% power to detect an improvement in median OS from 9 to 12 months using a log rank test with a final twosided alpha of 0.0322. It is estimated that approximately 500 patients will need to be recruited over 72 months, with a 1 year additional follow-up period, in order to observe 430 deaths. This includes an adjustment to take account of an assumed 5% of patients who will be lost to follow-up and for whom a date of death is not recorded.

## 10.2 STATISTICAL ANALYSIS PLAN

The statistical analysis plan will be written based on the final protocol and will be updated, as required, in association with any protocol amendments. The plan will include tables, listings and graphs and describe statistical programming considerations.

#### 10.2.1 Populations and Sub-Arms

- Intent to Treat population
- All randomized patients will be analyzed according to the treatment group to which they are assigned.
- Per Protocol Population (PPP)

All randomized patients will be analyzed according to the treatment actually received and adherence to the protocol. Patients who are determined to have major protocol violations as defined in Section 14 will be excluded from the PPP analysis

Safety Analysis Population (SAP)

All randomized patients who received study treatments at least once will be analyzed according to the treatment actually received.

#### 10.2.2 TRIAL ENDPOINTS

#### 10.2.2.1 PRIMARY EFFICACY ENDPOINT

The primary study endpoint is overall survival (OS) time, which will be calculated as the interval between the randomization date and the date of death for any cause, with censoring at the date of last contact for patients alive at last contact.

#### 10.2.2.2 SECONDARY STUDY ENDPOINTS

Time-to-progression will be compared between treatment and control arms from time of randomization to radiological progression (including new liver lesions and extra-hepatic lesions) according to RECIST v 1.1, modified RECIST and EASL criteria (see Appendix 5), assessed separately by investigator determination.

Time-to-symptomatic-progression will be compared between treatment and control arms from randomization to symptomatic progression. Symptomatic progression is defined as clinical progression to ECOG performance status ≥2. Such deterioration in PS should be observed at one subsequent evaluation 8 weeks later.

Tumor Response according to RECIST v 1.1, modified RECIST and EASL response criteria based on investigator assessment. At Baseline, target tumors are identified, and quantitative and qualitative (enhancement, necrosis) characteristics recorded. At all subsequent follow-up visits, the images (using the same modality) for the same target lesions will be read, and quantitative and qualitative characteristics recorded. Comparing these findings for follow up visits to the baseline findings, tumor response according to RECIST v1.1, modified RECIST or EASL criteria will be determined under separate analyses. Appendix 5 provides a summary of these criteria.

Patient Reported Outcome Assessments (including Functional Assessment of Cancer Therapy – Hepatobiliary Questionnaire - FACT-Hep). Patients will be asked to complete the questionnaire at Baseline and each of the 8 week study visits.

Safety will be assessed at all visits for enrolled patients using v 4.0 of the National Cancer Institute's Common Terminology for Adverse Events (NCI: CTAE). All adverse events, serious adverse events, and unanticipated adverse device effects as defined by the study protocol will be collected throughout the duration of the study. These events will be documented and recorded on the Adverse Event eCRF using the NCI Common Toxicity Criteria for Adverse Events; CTCAE v. 4.0 standards, and will be coded using the Medical Dictionary for Regulatory Activities (MedDRA).

#### 10.2.3 EFFICACY ANALYSIS

The efficacy analyses will be performed on the ITT and PPP populations.

#### 10.2.3.1 PRIMARY ENDPOINT STATISTICAL ANALYSIS PLAN

The Kaplan-Meier method will be used to estimate the OS curves in the two treatment arms; comparison between the curves will be performed using the log-rank test.

Interim Analyses: Two interim analyses of OS are planned to be performed by the Independent Data Monitoring Committee (IDMC) based on group sequential stopping rules using an alpha boundary defined by the rho family error spending function with rho=1.5. The first interim analysis is planned at approximately, but no less than, 125 deaths, with a two-sided p-value ≤0.0177 allowing the study to be stopped early for efficacy. A second interim analysis is planned at approximately, but no less than, 188 deaths, with a twosided p-value ≤0.0228 allowing the study to be stopped early for efficacy.

A conditional power of less than or equal to 15% at each of the interim analyses will result in the study stopping early for futility, using the method described in Proschan et al (2006).

Sample size modification will be considered at the second interim analysis using the approach described in Mehta and Pocock (2011). The exact criteria to allow sample size modification will be provided in the IDMC charter.

Final Analysis: The final analysis, without a sample size modification, is planned when approximately, but no less than, 250 deaths have occurred. A two-sided p-value ≤0.0322 is required to declare a statistically significant improvement in median OS at the final analysis.

If the sample size is increased after the second interim analysis, the final analysis is planned when approximately, but no less than, 430 deaths have occurred, which will result in 80% power to detect an improvement in median OS from 9 to 12 months using a log rank test with a final two-sided alpha of 0.0322.

#### 10.2.3.2 SECONDARY ENDPOINT STATISTICAL ANALYSIS PLAN

For secondary efficacy endpoints, each comparison between treatment groups will be conducted at the final analysis with α=0.05 (two-sided). Secondary study endpoints will be analyzed only at the final analysis to determine the statistical significance, if any between, the Treatment and Control groups.

- Time to progression (TTP) will be calculated as the interval between the randomization date and the date of first disease progression as defined by the respective criteria noted below, death for any cause or of last contact for patients alive. The Kaplan-Meier method will be used to estimate the TTP curves in the two treatment arms; comparison between the curves will be performed using the log-rank test. Median TTP will be reported. Progression will be assessed separately using:
  - RECIST v1.1 criteria
  - mRECIST criteria
  - EASL response criteria (assessed bidimensionally on enhancing tissue)
- Time to symptomatic progression (TTSP) will be calculated as the interval between the randomization date and symptomatic progression, defined as assessment of ECOG performance status ≥2 with or without tumor progression based on imaging. Deterioration in performance status is to be observed at one subsequent evaluation 8 weeks later. For subjects who had not progressed symptomatically at the time of analysis, TTSP will be censored at their last date of PS assessment. The Kaplan-Meier method will be used to estimate the TTSP curves in the two treatment arms; comparison between the curves will be performed using the log-rank test. Median TTSP will be reported.
- Tumor response rate. The response probability will be estimated in each of the two treatment arms as proportion of CR+PR over the total number of ITT or PPP patients. The disease control rate (ie, CR+PR+SD) will also be compared between the treatment arms. The minimum time between image acquisitions is 6-8 weeks. Tumor response rate will be assessed separately using:
  - RECIST v 1.1
  - mRFCIST
  - EASL

Tumor response will be compared using the continuity adjusted Newcombe-Wilson test, and the 95% confidence limits will be calculated

Patient reported outcome (PRO). The total score FACT-Hep will be calculated, the scores of each domain and each question at each time-point and their differences from baseline will be summarized for each treatment arm. The two treatment arms will be compared applying a mixed linear model with the treatment as factors, the baseline score and the relative time from baseline as covariates. A deterioration in QoL is defined as a 7-point decline in the total score or death whichever occurs first. The time to deterioration in QoL (TTDQoL) will be calculated as the interval between the randomization date and deterioration in QoL. The Kaplan-Meier method will be used to estimate the TTDQoL curves in the two treatment arms and will be compared using a log-rank test

A detailed description of data censoring handling for patients will be defined in the Statistical Analysis Plan.

### 10.2.4 SAFETY ANALYSIS

The safety analyses will be performed on the SAP population.

All treatment emergent adverse events (TEAEs), (defined as events which were not present at baseline or worsened in severity following the start of treatment) will be reported according to NCI Criteria. The incidence of TEAEs will be summarized according to the MedDRA coded primary system-organ class (SOC) and preferred term. The summaries will be presented overall (severity grades 1-5) and for grade ≥3 events and by treatment discontinuation. These summaries will present the number and percentage of patients reporting an adverse event for each classification level as well as the number of events reported.

Serious adverse events (SAEs) will be tabulated by treatment group.

Laboratory values will be summarized by treatment group over time and overall.

### 10.2.5 OTHER ANALYSES

The number of randomized patients, the number of patients treated, the number of patients in each analysis population will be summarized. Also the number of patients discontinuing from active treatments and reasons for discontinuation will be summarized. In the same manner the number of patients discontinuing follow up and reasons for discontinuations will be reported.

Listings of reasons for discontinuation from active treatments, from follow up, and reasons efficacy data cannot be evaluated in PPP will be also provided.

Duration of follow up will be described by descriptive statistics such as median and interquartile range.

Demographic, patient and disease characteristics will be listed and summarized using appropriate descriptive statistics.

Multi-variate Cox regression analysis of time-to-event efficacy endpoints will be conducted on AFP level, age, gender, naïve or recurrent disease, HCC diagnosis present at first oncology diagnosis, prior treatment, geography to determine the impact of these factors on trial endpoints.

As a sensitivity analysis, to address the poolability of data across regions (ie, Europe, North America or Asia), study sites and gender, a Cox regression analysis of the primary efficacy endpoint, OS, will be conducted with factors of region, study site and gender, and to determine the impact of these factors on OS. Note: region and study site will not be included simultaneously in the model due to collinearity.

Should the impact of region, site or gender on OS be statistically and clinically relevant, the reasons for the observed differential treatment effect, such as patient demographic or clinical characteristics, will be investigated and reported. If the poolability of OS results are in direct question as a result of this sensitivity analysis, the primary endpoint (OS) will also be analyzed separately by region, site or gender. The specific

mechanism of merging low enrolling study sites into virtual sites for purposes of analysis will be detailed in the Statistical Analysis Plan.

AFP levels at Q8 week visits for patients with AFP >400ng/mL at screening will be compared, in separate analyses, to RECIST v 1.1, mRECIST and EASL response criteria to correlate biological and radiological response to explore the use of variations in AFP as a confirmation of radiological response.

Analyses of all primary and secondary endpoints will be performed in a descriptive manner only using the following subgroups:

- Right vs left vs both branch PVT
- Ipsilateral vs contralateral tumor/PVT location

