#### Analysis of secondary efficacy endpoints

Comparison between treatment groups for all secondary endpoints will be conducted at the final analysis with a two-sided alpha of 0.05.

Time to event endpoints (ie, TTP, TTSP, Time to worsening of PVT) will be compared between treatment arms using a log-rank test. Tumor response rates will be compared between treatment arms using the continuity adjusted Newcombe-Wilson test. The

FACT-Hep score will be compared between treatment arms using a mixed linear model with baseline score and the relative time from baseline as covariates.

Safety Analysis: All patients who received study treatments at least once will be included in the safety analysis. All adverse events will be reported according to the National Cancer Institute Common Terminology Criteria for Adverse Events v 4.0 (CTCAE) grades and coded using the Medical Dictionary for Regulatory Activities (MedDRA). The incidence of treatment-emergent adverse events (events which were not present at baseline or worsened in severity following the start of treatment) will be summarized according to MedDRA primary system-organ class (SOC) and preferred term . Laboratory values will be summarized by treatment group over time and overall.

Poolability and Other Analysis: Multivariate Cox regression analysis of time-to-event efficacy endpoints will be conducted on stratification criteria and other factors such as age, gender, duration of disease prior to randomization.

As a sensitivity analysis, to address the poolability of data across regions (ie, Europe, North America, Asia), study sites and gender, a Cox regression analysis of the primary efficacy endpoint, OS, will be conducted with factors of region, study site and gender, and to determine the impact of these factors on OS. Note: region and study site will not be included simultaneously in the model due to collinearity.

Should the impact of region, site or gender on OS be statistically and clinically relevant, the reasons for the observed differential treatment effect, such as patient demographic or clinical characteristics, will be investigated and reported. If the poolability of OS results are in direct question as a result of this sensitivity analysis, the primary endpoint (OS) will also be analyzed separately by region, site or gender.

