The trial was stopped following a pre-specified second interim analysis for survival disclosing a statistically significant advantage for sorafenib [median 10.7 vs. 7.9 months; HR: 0.69 (95% CI: 0.55, 0.87), p= 0.00058]. The final analysis of time-to-tumor progression (TTP) by independent radiologic review was based on data from an earlier time point and demonstrated a statistically significant improvement in TTP in the sorafenib arm [median 5.5 vs. 2.8 months; HR: 0.58 (95% CI: 0.45, 0.74), p=0.000007]. In a subset analysis, patients with macrovascular invasion, the hazard ratio for OS favored sorafenib over placebo: HR 0.68 (95% CI 0.49 – 0.93).

To obtain regulatory approval in China a parallel study of sorafenib was undertaken in the Asia-Pacific region, where chronic hepatitis B virus infection is an important etiology factor. In 23 sites in China, Taiwan and Korea, Child Pugh A status patients were randomized in a 2:1 ratio to receive sorafenib (400 mg) or placebo twice daily in 6 week cycles. Of the 271 enrolled patients, 226 were randomized to receive placebo (N=76) or sorafenib (N=150). Demographic and baseline characteristics were similar in both arms as was hepatitis virus status: HBV infection was more common (70.7% sorafenib v.s 77.6% placebo) than HCV infection (10.7% sorafenib vs. 3.9% placebo).

Median overall survival was 6.5 months (95% CI 5.56 - 7.56) with sorafenib compared to 4.2 months (95% CI 3.75 - 5.46) with a hazard ratio of 0.68 (95% CI 0.5 - 0.93)[p=0.014]. Median TTP was 2.8 months (95% CI 2.63—3.58) in the sorafenib group compared with 1.4 months (95% CI 1.35—1.55) in the placebo group (HR 0.57 [95% CI 0.42—0.79]; p=0.0005). Adverse events and efficacy endpoint hazard ratios were consistent with those reported in the SHARP study, indicating similar action of sorafenib in both populations. Subsequent exploratory sub-set analyses in patients with macrovascular invasion and extra hepatic metastases, showed median OS of 5.6 months with sorafenib vs. 4.1 months with placebo; HR 0.75 (95% CI 0.54 - 1.05) and median TTP of 2.7 months with sorafenib vs. 1.3 months placebo; HR 0.58 (95% CI 0.41-0.83).

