7.2 Adjustments for Covariates

The following covariates will be included, one at a time, in univariate Cox regression analysis of time-to-event efficacy endpoints, including OS

Stratification factor (AFP \u226400 ng/mL vs \u226400 ng/mL

Notes:

Stratification factor of AFP according to the master file will be used even if the stratification factor was incorrectly recorded at randomization.

Site is also a stratification factor in this study. However, due to early termination of the study and small number of subjects per site, site will not be included as a covariate in this analysis since it would likely result in non-convergence of the model.

- ECOG status at baseline
- Age
- Gender
- Region (North America, Europe, Asia)
- Naïve or recurrent disease
- HCC diagnosis present at first oncology diagnosis
- Prior oncologic treatment for HCC (none, local regional therapy, prior resection, or systemic treatment)
- Duration from date of initial diagnosis of HCC to randomization
- Percent Tumor replacement at baseline
- HCC etiology (alcoholism, hepatitis B, hepatitis C, afloxatin-contaminated food, non-alcoholic cirrhosis, diabetes and other (including unknown))
- ALBI score (1, 2 or 3) at baseline

These covariates will also be included, one at a time, in a logistic regression analysis of binary efficacy endpoints.

All factors in the univariate models with a two-sided p-value <0.15 will be included in a multivariate analysis to determine the impact of these factors.

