7.5 Multi-center Studies and Pooling of Centers

This is a multi-center study; the data from all sites will be pooled according to treatment group.

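### The Protocol's poolability check tests whether region, site or gender is related to survival but reads the answer as a difference in treatment effect; neither document specifies an interaction test

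*Protocol*

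**What the plan says.** Protocol 10.2.5 describes a sensitivity analysis of poolability across Europe, North America and Asia, across sites and across gender. The Cox model for OS "will be conducted with factors of region, study site and gender, and to determine the impact of these factors on OS". Region and site are not to be in the same model. The text does not name treatment as a term, or any product of treatment with a factor. The follow-up rule is "Should the impact of region, site or gender on OS be statistically and clinically relevant, the reasons for the observed differential treatment effect" will be investigated. A second step follows: "If the poolability of OS results are in direct question as a result of this sensitivity analysis", OS is also analysed by region, site or gender. No criterion is given for that step. The synopsis repeats the rule: "a Cox regression analysis of the primary efficacy endpoint, OS, will be conducted with factors of region, study site and gender". Protocol 10.2.5 leaves to the SAP how small sites are to be merged into virtual sites.

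The SAP, written after early termination, handles these factors differently:

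- **Section 7.2:** "The following covariates will be included, one at a time, in univariate Cox regression analysis of time-to-event efficacy endpoints, including OS". Region and gender are on the list. Site is left out because few patients per site would probably stop the model converging. Factors with p below 0.15 go into a multivariate model. No interaction with treatment is named.
- **Section 7.5:** "the data from all sites will be pooled according to treatment group". No check is attached and no merging rule is given.
- **Section 7.7:** no subgroup analyses, because of the limited number of patients.
- **Section 5 (changes to the plan):** lists early termination, the loss of the interim analyses and the handling of death in TTP. It does not mention the poolability check.

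**The concern.** Whether a factor is related to OS is a question about prognosis. Whether TheraSphere against sorafenib works differently across levels of that factor is a question about a treatment-by-factor interaction. The Protocol tests the former and words its conclusion as the latter.

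The Protocol's own background (5.3) shows how the two can part. In the mainly European and North American sorafenib trial, OS was "median 10.7 vs. 7.9 months; HR: 0.69" against placebo. In the Asia-Pacific trial, "Median overall survival was 6.5 months (95% CI 5.56 - 7.56) with sorafenib compared to 4.2 months" on placebo, with HR 0.68. Sorafenib survival differed by about four months between the trials, while the relative effect was nearly the same.

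Two errors are possible. A regional difference in prognosis could be reported as a difference in treatment effect and lead to separate analyses that nothing about the treatment calls for. Or a genuine difference in effect, which matters for a catheter-delivered device used at up to 25 centres on three continents, could pass unnoticed.

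**Working it through.** **The plan's own figure.** The poolability check has no stated operating characteristics. The OS design around it reproduces. HR = 9/13 = 0.692. Rho-family spending with rho = 1.5 at information 0.50, 0.75 and 1.00 gives two-sided boundaries of 0.0177, 0.0228 and 0.0322, as stated. Power at 250 deaths is 79.95% against the stated 80%. The sample size is 250/0.836/0.95 = 315 against 320. So 250 deaths is a sound basis for what follows.

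**Assumptions not in the documents.** Two regions; exponential survival; treatment included in the Cox model; a share w of patients (and deaths) from the second region, varied from 15% to 50%. The regional medians are borrowed from the two background trials, which differ in more than region, so they illustrate and do not predict.

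**1. Prognostic gap only, same treatment effect.** Region HR = 10.7/6.5 = 1.65, ln = 0.498. The chance of a significant main effect at two-sided 0.05 is about Φ(|ln HR|·√(D·w·(1−w)) − 1.96), with D = 250:

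| w | √(D·w·(1−w)) | Region HR 1.65 | Region HR 0.80 (abs. ln = 0.223) |
|---|---|---|---|
| 0.15 | 5.65 | 80% | 24% |
| 0.20 | 6.32 | 88% | 29% |
| 0.25 | 6.85 | 93% | 33% |
| 0.50 | 7.91 | 98% | 42% |

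Simulation agrees: 2,000 trials per scenario, 320 patients accrued over 42 months, cut at the 250th death, treatment HR 0.692 in both regions. The main effect was significant in 95.7% (w = 1/3) and 97.7% (w = 1/2) of trials. The treatment-by-region term was significant in 4.9% and 4.7%, its nominal rate.

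**2. Real difference in effect, equal average prognosis.** Each region's medians are centred on √(9×13) = 10.8 months: control 10.8·√HR, treated 10.8/√HR. With HR 0.50 in one region and 1.00 in the other, the medians are 7.6 and 15.3 months, and 10.8 and 10.8 months.

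| HRs by region | Main effect significant | Interaction significant |
|---|---|---|
| 0.50 and 1.00 | 5% to 6% | 74% to 77% |
| 0.55 and 0.87 | about 5% | 39% to 44% |

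**3. Real difference in effect, equal control medians.** With control medians of 9 months in both regions and HR 0.50 against 1.00, the treated arms differ (18 against 9 months). The main effect is significant in 66% to 70% of trials and the interaction in 74% to 78%. So the main-effect test is not always blind to a real difference, but its result looks the same as under step 1.

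**4. Power of the interaction test.** SE = √(4/(D·w) + 4/(D·(1−w))) = 2/√(D·w·(1−w)). For a ratio of HRs of 13/9 = 1.44 (ln = 0.368) and D = 250, w = 0.20 gives SE 0.316 and power 21%; w = 0.50 gives SE 0.253 and power 31%. The documents do not give the deaths at termination. If there were 60, the same formula gives about 9% to 11%.

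**The case against.** The best defence has five parts.

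- **The primary result is not at risk.** A reader might infer that the rule decides whether the trial's single OS answer stands or is split. It does not. The check is labelled a sensitivity analysis, the separate analyses are additional, and the pooled log-rank comparison stays primary. This stands.
- **Significance alone does not trigger the separate analyses.** A reader might infer from step 1 that pooling would usually be called into question. The factor's impact must also be clinically relevant, and poolability must then be judged doubtful. The percentages count p-values below 0.05, not triggered analyses. This stands, so the claim is that a prognostic gap could mislead, not that it would.
- **The SAP removes the consequence.** Sections 7.5 and 7.7 pool all sites and make no subgroup analyses, so no false split can occur in the terminated trial. This stands for the false trigger. It does not answer the missing interaction test or the silence in Section 5.
- **Site is explained.** SAP 7.2 gives a convergence reason for dropping site, which goes some way to explain the absent virtual-site rule. This largely stands.
- **The wording shows that an interaction was intended.** It may have been. Then the specified model leaves out the one term that answers the question, and the text needs the same correction.

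A reader might also infer that the check cannot detect a difference in effect. Step 3 shows that it sometimes would. The accurate criticism is that it is non-specific, and blind only when average prognosis balances.

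**Conclusion.** The point holds as a defect in the Protocol's rule and a gap in the SAP. Protocol 10.2.5 and the synopsis draw a conclusion about effect modification from a test that cannot distinguish it from prognosis.

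The size depends on assumptions. If the background sorafenib medians applied by region, a purely prognostic gap would give a significant main effect in about 80% to 98% of trials at 250 deaths, against about 5% for the interaction. At a prognostic HR of 0.80 the figure falls to about 29% to 42% for shares of 20% to 50% (24% at a 15% share), still well above 5%. In the other direction, a difference as large as HR 0.50 against 1.00 is flagged in only 5% to 6% of trials if regions share the same average prognosis.

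The documents do not support reading this as a threat to the primary OS comparison, or as a distortion of the final analysis through false splitting. For the terminated trial, what remains is that no analysis addresses consistency of effect across regions or gender, and that a pre-specified check disappeared without being recorded.

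**What to change.** 1. **Model.** In Protocol 10.2.5, the synopsis and SAP 7.5, base the check on treatment-by-region and treatment-by-gender terms, in a Cox model for OS that also contains treatment and the factor's main effect. Report the OS HR with its 95% CI by region and by gender.
2. **Wording.** Delete the reading of a main effect of region, site or gender as a differential treatment effect. Main effects can still be reported as prognostic findings.
3. **Site.** Given the convergence concern in SAP 7.2, assess site only through merged sites or a random effect, if estimable. Otherwise state that variation in effect by site is not assessed.
4. **SAP 7.7.** Note that the HRs by region and gender are a consistency check and an exception to the exclusion of subgroup analyses.
5. **Record.** Add to SAP Section 5 that the Protocol's poolability check was dropped or replaced, and why.

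The cost is one SAP paragraph and a few lines of code, with no new data. The downside is the low power shown in step 4 of the working, lower again after early termination. The results should be labelled descriptive, and a non-significant interaction should not be presented as evidence that the effect is uniform.
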